### 8.4. Neuropsychological Test Battery (NTB)

The NTB consists of TMT A and TMT B, Digit Span, COWAT, and CFT. The TMT A and TMT B marking duration in seconds, Digit Span, CFT, and COWAT, tests will be summarized by visit and treatment. The composite scores for each item defined in Section 6.1.8 will be summarized by visit and treatment.

[figure not shown]
The change from baseline for each NTB component score will be analyzed using the same MMRM model described in Section 8.1.

For the interim analysis, an ANCOVA model at each visit will be run using the same effects described in Section 8.1. For endpoints where LOCF is used, the analyses will be repeated using only observed data.

Results for NTB will also be listed.

#### 8.5. ADCS-Clinical Global Impression of Change (ADCS-CGIC)

The ADCS-CGIC was developed by the Alzheimer's Disease Cooperative Study (ADCS). The scale consists of a format with which a clinician may address clinically relevant overall change, including 15 areas under the domains of cognition, behavior, and social and daily functioning. The rater, at baseline, interviews the participant and caregiver/informant, using a form that comprehensively lists relevant symptoms potentially useful in judging change, and makes notes for future reference. There are few requirements to fulfill during the interview, but clinical assessment of mental status is to be made. By allowing raters to use the forms in an unstructured manner, this scale may facilitate clinical judgements with face validity. At follow-up visits, the

clinician uses a similar set of forms to re-interview the participant and caregiver/informant. The ADCS-CGIC rating is made on a 7-point scale similar to other global change scales, where a lower score indicates marked improvement. The ADCS-CGIC value is a measure of the change from baseline and therefore the algebraic change from baseline is not calculated for the ADCS-CGIC. As available at the site, the ADCS-CGIC will be completed by an independent rater (not the rater completing the cognitive or other assessments).

Descriptive numeric summaries of observed values in the ADCS-CGIC will be calculated by visit.

Observed values for ADCS-CGIC will be analyzed using the same MMRM model described in Section 8.1. Since an ADCS-CGIC result is not collected at baseline, no baseline covariate will be included in the model.

For the interim analysis, an ANCOVA model at each visit will be run using the same effects described in Section 8.1, with no baseline covariate in the model. For endpoints where LOCF is used, the analyses will be repeated using only observed data.

For the final analysis, ADCS-CGIC will be summarized and analyzed for both the mITT Population and the Completers Population. Additionally, the observed values for ADCS-CGIC will be summarized and analyzed for each subgroup defined in Section 6.1.10 using the mITT Population. For the subgroup analysis by ApoE status at Baseline, the APOE covariate will be excluded from the statistical model.

Results of ADCS-CGIC will also be listed.

Additionally, frequencies and percentages in the ADCS-CGIC will be summarized by visit. Cochran-Mantel-Haenszel mean score statistics, using rank scores, and stratified by ApoE status, will be used to assess the difference in ADCS-CGIC responses at each visit between the CT1812 dose levels and placebo.

[figure not shown]

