  - This blood draw will be performed at a local lab. The local lab will include onsite laboratory facilities for collection and processing. Participants consented to Protocol version 2.0 on or after their Baseline visit are not required to have the Biomarker samples drawn on Day 90 or Day 172.
- 19. The serum samples should not be collected on the same day as the lumber puncture.
- 20. Coagulation testing includes prothrombin time and INR.
- 21. Optional lumbar puncture: Participants may opt to undergo lumbar puncture as part of screening, after all other eligibility criteria have been reviewed and approved by the medical monitor, at least 24 hours before the Baseline visit and again at Day 182 (the end of the dosing period). LP on the Day 182 visit should be performed minimally 24 hours prior to the other the Day 182 visit procedures (e.g., Day 181) and prior to dosing on that day. The optional screening visit lumbar puncture must not be performed without Medical Monitor approval.
- 22. Urine should not be first morning void. See Laboratory Procedures Manual for sample handling.
- 23. Pregnancy testing should include an assessment of FSH levels.
- 24. C-SSRS Screening/Baseline version used at screening visit, Since Last Visit version used at all other visits.
- 25. The ADAS-Cog 13, NTB, ADCS-ADL, and MMSE will be conducted during screening period, and prior to dosing at other visits. The ADCS-CGIC will be conducted beginning at Day 1, and all other visits with the cognitive assessments.
- 26. All concomitant medications will be recorded from screening through Day 210.
- 27. During Screening (post-consent), only SAEs related to a study-specific procedure will be collected. For all related AEs of moderate or severe intensity ongoing at the end of the study, follow-up will continue until the event has resolved to baseline severity, the event is assessed as stable by the Investigator, or the participant is lost to follow-up or the participants withdraws consent.
- 28. Study drug accountability will be performed via capsule count.
- 29. Dosing on non-study visit days will be self-administered at home. On "Drug Dispensation" clinic visits drug accountability will be completed for the bottle returned by the participants and the "in office dose administration" will be taken for that visit from the newly assigned bottle. Study drug can be administered with, or without food.

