#### 5. Analysis Populations

The following analysis populations are planned for this study:

- All Subjects: The All Subjects population includes all participants who sign the ICF and get screened for the study.
- Safety Population (SAF): The Safety Population includes all participants who receive one or more doses of study medication.
- Efficacy Modified Intent-To-Treat Population (mITT): The Efficacy mITT Population includes all randomized participants who receive any amount of study drug and who have a baseline and at least one post-baseline assessment of the ADAS-Cog 11 total score.
- Completers Population (CP): The Completers Population includes all randomized participants who completed the study (i.e., who did not prematurely withdraw). There is no expectation that a participant included in the CP will have attended every single scheduled visit; as long as the participant completed the study, they will be included in the population.
- **Pharmacokinetic Population (PK):** The Pharmacokinetic Population includes all participants in the SAF who had at least one quantifiable concentration of CT1812.

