#### 8.1. Composite z-scores

The composite z-scores (Cognitive Composite score; Memory Composite score; Attention Composite score; and Executive Function Composite score) defined in Section 6.1.8 will have their observed values and change from baseline summarized by visit.

Mean change from baseline within each of the four composite z-scores will be analyzed using a MMRM analysis with treatment as the main effect, visit, baseline z-score of the corresponding composite score, APOE  $\varepsilon 4$  (+ or -) status at baseline, and treatment by visit as an interaction term. All post-baseline analysis visits will be included in the model (Day 42, Day 98, and Day

182). An unstructured covariance matrix will be used to model the within-participant errors. The Kenward-Roger approximation will be used to estimate degrees of freedom.

The least squares (LS) mean change from baseline will be presented along with the associated 95% Confidence Interval (CI) within each treatment group. In comparing treatments (CT1812 100 mg/day minus placebo, CT1812 300 mg/day minus placebo, and the CT1812 groups combined versus placebo), LS mean differences in change from baseline will be presented along with associated 95% CIs and pairwise treatment *P*-values.

In the case of convergence issues, other covariance structures will be considered including (but not limited to) Toeplitz, compound symmetry (CS) and autoregressive (AR[1]) with each model fit to find the covariance structure with the best fit. The fit statistics will be compared for all covariance structures and the structure with the smallest Akaike information criterion will be retained as the preferred model.

For the interim analysis, ANCOVA model at each visit will be run in place of the MMRM. This model will include treatment as the main effect, baseline z-score of the corresponding composite scores, and APOE  $\varepsilon 4$  (+ or --) status at baseline. For endpoints where LOCF is used, the analyses will be repeated using only observed data.

The composite z-scores will also be listed.

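### The final ADCS-CGIC model leaves out baseline severity because the scale has no baseline of its own; adjusting for baseline ADAS-Cog 11 is possible, costs almost nothing and may improve precision

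*SAP*

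**What the plan says.** SAP 8.5 takes its model from elsewhere: "Observed values for ADCS-CGIC will be analyzed using the same MMRM model described in Section 8.1". SAP 8.1 specifies an "MMRM analysis with treatment as the main effect, visit, baseline z-score" of the relevant score, APOE ε4 status, "and treatment by visit as an interaction term". Section 8.5 then removes the baseline term: "Since an ADCS-CGIC result is not collected at baseline, no baseline covariate will be included in the model". The interim ANCOVA for this scale likewise has no baseline covariate.

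APOE ε4 status stays in the main model, since the section removes it in one situation only: "For the subgroup analysis by ApoE status at Baseline, the APOE covariate will be excluded from the statistical model". The supporting categorical test uses "Cochran-Mantel-Haenszel mean score statistics, using rank scores, and stratified by ApoE status", so it has no severity term either.

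Severity is measured before treatment. The notes to SAP Table 1 state: "The ADAS-Cog 13, NTB, ADCS-ADL, and MMSE will be conducted during screening period, and prior to dosing at other visits". The table schedules these assessments at screening and on Day 1. SAP 5 limits the mITT population to treated, randomised participants "who have a baseline and at least one post-baseline assessment of the ADAS-Cog 11 total score".

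**The concern.** The reason given for having no baseline covariate explains only why ADCS-CGIC cannot be adjusted for itself. It does not explain why no measure of severity is used. The MMSE, ADAS-Cog and ADCS-ADL models (SAP 8.2, 8.3 and 8.6) each include a baseline score. ADCS-CGIC is left with treatment, visit, their interaction and a genotype. Neither Protocol 7.5 nor SAP 3.5 names a stratification factor for randomisation, so the design as described does not balance severity either.

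What is at stake is precision. If baseline severity predicts the global rating, the residual variance is larger than it need be, and the confidence interval for ADCS-CGIC is wider than the data already being collected would allow.

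**Working it through.** **Inputs from the documents.** SAP 3.2 gives 48 per group and 15% dropout, with SD 5.4 and difference 3.0 for ADAS-Cog 11. SAP 3.5 gives 1:1:1 allocation. SAP 4.2 gives 24 participants at the interim. No SD, effect size or power is stated for ADCS-CGIC.

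**Assumption.** r is the within-arm correlation of baseline severity with ADCS-CGIC. It is not in the documents, so it is varied from 0 to 0.5. Only r² enters, so the direction of scoring does not matter.

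**Step 1: reproduce the plan's figure, to fix the analysed sample size.** 48 × 0.85 = 40.8 on placebo and 81.6 on pooled CT1812. The standard error is 5.4 × √(1/40.8 + 1/81.6) = 1.035, and 3.0/1.035 = 2.897. Power = Φ(2.897 − 1.960) = 82.6%, or 82.0% with the t distribution. With 40 and 80 analysed, the t version gives 81.2%. The stated 81% is reproduced to within 2 points. The analysed total is therefore 3 × 40.8 = 122.4.

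**Step 2: effect of one added covariate at the final analysis.** The ratio of the adjusted to the unadjusted standard error is

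√[(1 − r²) × (1 + 1/(df − 2))], with df = 122.4 − 4 = 118.4 (three arms and APOE).

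The second factor, 1 + 1/116.4 = 1.0086, is the cost of estimating the extra coefficient. Power is shown for a comparison that has 80% power unadjusted: Φ(2.802/ratio − 1.960). Equivalent N is 122.4/ratio².

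| r | SE ratio | SE change | Power | Equivalent N |
|---|---|---|---|---|
| 0 | 1.004 | +0.4% | 79.7% | 121 |
| 0.1 | 0.999 | −0.1% | 80.1% | 123 |
| 0.2 | 0.984 | −1.6% | 81.3% | 126 |
| 0.3 | 0.958 | −4.2% | 83.3% | 133 |
| 0.4 | 0.920 | −8.0% | 86.1% | 145 |
| 0.5 | 0.870 | −13.0% | 89.6% | 162 |

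Break-even: r² = 1 − 1/1.0086 = 0.0085, so |r| is about 0.09.

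**Step 3: check by simulation.** A single-visit simulation of a score rounded to seven points, with 41 per arm and 6,000 runs per value of r, gave SE ratios of 1.004 (r = 0), 1.000 (0.1), 0.985 (0.2), 0.962 (0.3) and 0.881 (0.5). These are close to the formula.

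**Step 4: the same formula at the interim.** With 24 participants, df = 24 − 4 = 20 and the cost factor is 1 + 1/18 = 1.056. At r = 0 the SE rises by 2.7% (√1.056 = 1.027). At r = 0.2 it still rises, by 0.7% (√(0.96 × 1.056) = 1.007). Break-even: r² = 1 − 1/1.056 = 0.053, so |r| is about 0.23.

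The formula and the simulation treat one visit at a time. They approximate the Day 182 contrast in the repeated-measures model and do not reproduce the full model.

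**The case against.** The strongest reply is that this is a deliberate choice, with a stated reason, on an exploratory endpoint, and that no benefit has been shown. Much of that stands:

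- **No bias.** A reader might infer that the unadjusted ADCS-CGIC estimate is biased by severity imbalance. The documents do not support that. Treatment is randomised, and ordinary chance imbalance is already reflected in the standard error.
- **No proven loss.** A reader might infer that precision is certainly being given up. That would need a value of r, and the documents give none. A low r is plausible: ADCS-CGIC is already rated relative to each participant's own starting point, and entry MMSE is restricted to 18–26.
- **APOE is not dropped.** Taken alone, the statement about no baseline covariate could suggest a model with no covariates at all. The rest of Section 8.5 shows that APOE ε4 status remains.
- **The interim.** Extending the adjustment to the interim ANCOVA could make that estimate less precise, as step 4 shows.
- **Severity is not ignored.** ADCS-CGIC is also analysed by baseline MMSE subgroup (18–21 and 22–26, SAP 6.1.10). This shows results by severity, but it does not adjust the main comparison.
- **Little depends on it.** SAP 6.1.3 treats the ADCS-CGIC p-values as nominal and outside the fixed testing sequence, and no design claim rests on this scale.

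What the reply does not do is defend the stated reason. The absence of an ADCS-CGIC baseline is no argument against a severity covariate that the trial already collects. At the final analysis the worst case is a 0.4% larger standard error, so the unknown r is not a good reason to leave it out.

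**Conclusion.** The point holds as a minor improvement. The stated reason does not justify omitting severity, and the covariate is guaranteed for mITT. At the final analysis the possible gain outweighs the cost: at worst +0.4% in standard error, against −1.6% to −8.0% for r between 0.2 and 0.4, with nothing gained below |r| of about 0.09.

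This rests on about 122 participants analysed, on an assumed r, and on a single-visit approximation. It should be described as precision that may be given up. It is neither a bias nor a demonstrated loss, and it does not affect the primary exploratory analysis of ADAS-Cog 11. The guarantee of availability does not extend to the Completers Population, whose definition in SAP 5 does not require a baseline ADAS-Cog 11.

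**What to change.** In SAP 8.5, before unblinding for the final analysis, replace the sentence on the baseline covariate. The new text should say that the final-analysis ADCS-CGIC repeated-measures model includes baseline ADAS-Cog 11 total score as its single added covariate, with the other Section 8.1 terms, including APOE ε4 status, unchanged. Name one scale only. A choice between ADAS-Cog 11 and MMSE would leave a decision open in a plan meant to be fixed in advance, and mITT membership guarantees ADAS-Cog 11. Leave the interim ANCOVA as it is.

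The cost is one sentence, one model term and one degree of freedom, with no new data. In the Completers analysis, any participant without a baseline ADAS-Cog 11 would drop out of the model, and their number should be reported. If the sponsor prefers no severity adjustment, the SAP should give a reason other than the missing ADCS-CGIC baseline.

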#### 8.6. ADCS-Activities of Daily Living (ADCS-ADL)

The ADCS-ADL is a 23-item informant-administered assessment of functional impairment in terms of activities of daily living. Informants respond to 23 questions about the participant's involvement and level of performance across items representing daily living. The questions range from basic to instrumental activities of daily living. Each item is rated from the highest level of independent performance to complete loss. The total score range is from 0 to 78 with lower scores indicating greater functional impairment.

Descriptive summaries of observed values and changes from baseline in the ADCS-ADL total score will be calculated by visit.

Change from baseline for ADCS-ADL will be analyzed using the same MMRM model described in Section 8.1, with the ADCS-ADL score in place of the composite score.

For the interim analysis, an ANCOVA model at each visit will be run using the same effects described in Section 8.1, with baseline ADCS-ADL score in place of the composite baseline score. For endpoints where LOCF is used, the analyses will be repeated using only observed data.

For the final analysis, ADCS-ADL will be summarized and analyzed for both the mITT Population and the Completers Population. Additionally, the change from baseline in ADCS-ADL will be summarized and analyzed for each subgroup defined in Section 6.1.10 using the mITT Population. For the subgroup analysis by ApoE status at Baseline, the APOE covariate will be excluded from the statistical model.

Results of ADCS-ADL will also be listed.

#### 8.7. Cognitive Composite Score and its Components

Descriptive summaries of observed values and changes from baseline will be calculated by visit. The results will also be listed.

[figure not shown]
#### 8.8. Biomarker Changes

Targeted measurements of several protein biomarkers in CSF and plasma will be made, including the following:

Biology	Biomarker	Biofluid
	Αβ42, Αβ40, Αβ42/40 ratio	CSF, plasma
	Total Tau	CSF
AD progression disease	pTau181	CSF, plasma
	pTau217	plasma
	Brain derived Tau (BD-Tau)	plasma
	Neurogranin	CSF
Synaptic function	Synaptotagmin 1, SNAP25	CSF
Neuroinflammation	GFAP	CSF, plasma
Neurodegeneration	NFL	CSF, plasma
Other	Alpha-Syn	CSF

For A $\beta$ 40 and A $\beta$ 42, it is expected to see decreases in the change from baseline values with CT1812 treatment at 6 months. For all remaining biomarkers, it is hypothesized that changes will be observed over the 6-month treatment period.

Descriptive summaries of observed values and changes from baseline for each plasma and CSF

biomarker will be calculated by visit.

Plasma samples will be analyzed at baseline (V2), V11 (Day 98), and Day 182. Assuming data for more than one post-baseline sample is available, the change from baseline for each plasma biomarker will be analyzed using the same MMRM model described in Section 8.1. If only one post-baseline sample is available, then the ANCOVA model detailed below will be used.

For the interim analysis, for analysis of the CSF biomarkers at the final analysis, and in the scenario where only one post-baseline plasma biomarker sample is available at the final analysis, an ANCOVA model of change from baseline values will be run using the same effects described in Section 8.1. For CSF, only screening (V1) and V14 (Day 182) biomarker samples were collected and biomarkers will be measured in CSF from V1 and V14 and will be analyzed in the final analysis.

For the analysis of phospho-tau proteins performed for the interim analysis only, ANOVA analysis of the log2 (fold change from baseline) will be used to assess significance of drug effects.

For the final analysis, the change from baseline in each biomarker will be summarized and analyzed for the "Measurable PK at Multiple Timepoints" subgroup. Additionally, for just the A $\beta$ 40 and A $\beta$ 42 biomarkers, the change from baseline will be summarized and analyzed by the "MMSE at Baseline" subgroup. The following rules will apply to the subgroup analyses:

- If less than 10 participants fall into any one treatment group/level of a subgroup, then the corresponding summary/analysis for that subgroup will not be conducted.
- If at least 10 participants fall into all treatment groups/levels of the subgroup, then the corresponding summary/analysis for that subgroup will be conducted.
- These rules will be applied separately for the subgroup analyses which compare individual CT1812 dose groups vs. placebo and for those which compare the pooled CT1812 dose group vs. placebo. It is possible that these criteria will not be met for the analysis based on individual CT1812 dose groups, but once the CT1812 dose groups are pooled, the criteria are met.

For the final analysis, the following figures will be produced:

- Spaghetti plots displaying individual participant-level data of observed values over time for each plasma and CSF biomarker by treatment group (placebo, CT1812 100 mg, CT1812 300 mg). The mean value for each treatment group will be overlayed and presented as a bold line in the body of the figure. These will be formatted as 3-panel, side-by-side plots, where each treatment group is presented in their own panel and all on the same Y-axis.
- Line plots displaying the mean (±SD) observed values over time for each plasma and CSF biomarker by treatment group (placebo, CT1812 100 mg, CT1812 300 mg, pooled CT1812 100 mg+300 mg).
- Line plots displaying the mean (±SD) change from baseline values over time for each plasma biomarker by treatment group (placebo, CT1812 100 mg, CT1812 300 mg, pooled CT1812 100 mg+300 mg).
- Line plots displaying the mean (±SD) change from baseline values at Day 182 for each CSF biomarker by treatment group (placebo, CT1812 100 mg, CT1812 300 mg, pooled

Statistical Analysis Plan, Sponsor Cognition Therapeutics, Inc. Protocol Number COG0201 PCN Number COGN187880

CT1812 100 mg+300 mg) and plotted in this order from left to right in the figure.

- Line plots displaying the LS mean (±95% CI) change form baseline values for each
  plasma and CSF biomarker by treatment group (placebo, CT1812 100 mg, CT1812 300
  mg, pooled CT1812 100 mg+300 mg) and plotted in this order from left to right in the
  figure.
- Vertical scatter plots displaying the individual participant-level data of change from baseline values at Day 182 for each CSF biomarker by treatment group (placebo, CT1812 100 mg, CT1812 300 mg, pooled CT1812 100 mg+300mg) and plotted in this order from left to right in the figure.

All biomarker data will also be listed.

#### 8.9. Other Exploratory Efficacy Analyses

Pearson correlation coefficients will be used to assess associations between biomarkers and cognitive and behavioral changes (ADAS-13, ADAS-11, Memory Composite, Attention Composite, NTB individual items, Executive Function Composite, Cognitive Composite, MMSE, ADCS-ADL, and ADCS-CGIC). Correlations will be calculated for baseline biomarker values and baseline efficacy measures. Additionally, correlations between change from baseline in by-visit biomarker values and change from baseline in efficacy scales will be calculated, and correlations between observed values in by-visit biomarker values and observed values in efficacy scales will be calculated.

CT1812 concentrations in CSF and plasma will also be correlated with changes from baseline in biomarkers and cognitive measures.

Additional analyses and correlations may be explored as well (e.g., possibly including age, gender, education and ApoE) and will be discussed in the clinical study report (CSR).

